The 42-items questionnaire was developed originally in Danish in 1999 [51] and measures the structural aspect of social relations, with focus on contact frequency and diversity, and functional aspects with focus on perceived social support. CSRQ has been used in several Danish population-based surveys including in the Copenhagen Aging and Midlife Biobank (CAMB) [52]. In a sample of 38-69 old adults the CSRQ showed acceptable face and content validity and good test-retest reliability by 41% of the items had substantial to almost perfect agreement (kappa: 0.65-0.97) and the rest showed moderate agreement (kappa: 0.41-0.60) [53].

The secondary outcomes will also serve as follow up measurements six and 12 months after ending the intervention. They will also be conducted with online surveys.

13. Participant timeline

Time schedule of enrolment, interventions (including any run-ins and washouts), assessments, and visits for participants. A schematic diagram is highly recommended (see Figure).

[figure not shown]

Figure 1. SPIRIT participant timeline.

14. Sample size

Estimated number of participants needed to achieve study objectives is 128 participants. The number will be enough to show a 0.5 standard deviation difference between groups, equal to a moderate effect size. The number of participants will yield a power on 80% with a significance level on 0.05. To account for attrition this study will include 20% more participants than the above mentioned, and hence terminate the inclusion of participants when 154 participants in total and 77 in each group have been enrolled.

15. Recruitment

We will recruit participants through online advertisements on social media and in non-profit organizations working with older adults. We will also try to recruit participants at activity centers and other communities of older adults.

Methods: Assignment of interventions

16. Allocation

16.a. Sequence generation

Participants will be randomly assigned to either the intervention or the control group, with a 1:1 allocation. Eligible participants who have completed the baseline step count, will be randomized in blocks of four participants or more, stratified on sex (M/F) and average baseline step count for the extracted days prior to the allocation. Randomization of participants will happen every week, except weeks with less than four new participants.

16.b Allocation concealment mechanism

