The secondary outcomes are all participant reported and administered through SurveyXact. All participants will receive an email with an electronic SurveyXact invitation on the day of randomization. On the last day of intervention (day 84), the participants will receive a similar SurveyXact invitation with the end-point questionnaire. The six and 12-month follow up assessments will be administered in similar ways to the end-point assessment.

Demographic and other baseline items

Non-outcome variables will be included in the baseline questionnaire.

18b. Plans to promote participant retention and complete follow-up.

If possible, reasons for drop out will be collected from each discontinued participant. The available data on the primary outcome will be used to calculate the intervention period average steps per day. If the participant fails to synchronize the PAM and a possible drop out is suspected, a person from the research team will call the participant to either remind them to synchronize the PAM or try to motivate the participant to continue the intervention.

Lost to follow up with the end-point or follow up questionnaires will be reminded via email 7, 14 and 21 days after the deadline.

19. Data management

All outcomes will be handled and stored electronically.

Steps per day will be stored every time the participant synchronizes the PAM. The data handling responsible Fitrockr will extract data from the Garmin applications and store it according to the agreements. Every time a participant completes the intervention period, their data will be exported from the Fitrockr database and stored securely at the University of Copenhagen server.

During the study, with participants' verbal consent, telephone MI (and control) sessions is audiotaped on a regular basis to ensure fidelity of intervention delivery and to provide counselor feedback.

The participant reported outcomes for the secondary outcomes will be administered using SurveyXact, securing data every time a survey has been completed. Every time a participant completes the intervention period, their data will be exported from the Fitrockr database and stored securely at the University of Copenhagen server.

No personal data will be exported from Fitrockr or SurveyXact without pseudonymization. Complete anonymization of all data will be done after the last follow up period. Data protection agency approval Reference number: 514-0268/18-3000

20. Statistical methods

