The primary outcome will be analyzed as a mixed effects model, where intervention group are analyzed fixed and participants are random effects. The analysis will investigate the group difference in average daily step count, adjusted for baseline step count and gender. Same analysis will be performed on secondary outcomes.

Drop outs with data on the primary outcome for at least one week will have their average daily step count based on the available days. All analysis will be performed following the Intention to Treat (ITT) principle imputing missing data using a multiple imputation based on age, gender, baseline step counts and average daily step count (for missing data on the secondary outcomes). In

calculating the average daily step count, days with less than 100 steps will be handled as “days of non-wear” and excluded assessing the mean step count.

Methods: Monitoring

21. Data monitoring

Not applicable/relevant

22. Harms

In our study an adverse event will be defined as any untoward medical occurrence in a participant without regard to the possibility of a causal relationship with the intervention. Adverse events will be collected after the subject has provided consent and enrolled in the study. If a participant experiences an adverse event after the electronically administered informed consent has been signed (entry) but the subject has not started to receive study intervention, the event will be reported as not related to the intervention. All adverse events occurring after entry into the study will be recorded. The participants will be asked at the end-point questionnaire if they experienced any adverse events in terms of using the PAMs or trying to enhance their daily amount of physical activity.

23. Auditing

No auditing has been protocolled.

Ethics and dissemination

24. Research ethics approval

According to a written correspondence with the Danish Ethics Committee in the Capital Region of Denmark, this trial was not subject to the current laws on research ethics in Denmark due to the non-invasive behavioral change intervention. The study can be conducted without further approval from the Danish Ethics Committee in the Capital Region of Denmark (Journal-nr.:18004960).

25. Protocol amendments

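### The plan promises to record all adverse events but describes only one day-84 questionnaire item, and contacts with people who stop do not feed the harms record

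*Combined protocol and SAP*

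**What the plan says.** Section 22 (Harms) sets a broad definition: "an adverse event will be defined as any untoward medical occurrence in a participant", whatever the cause. It then makes an unqualified commitment: "All adverse events occurring after entry into the study will be recorded". The only collection step that follows is this: "The participants will be asked at the end-point questionnaire if they experienced any adverse events". The item is limited to events "in terms of using the PAMs or trying to enhance their daily amount of physical activity", which is narrower than the definition.

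Section 18a fixes the timing: "On the last day of intervention (day 84), the participants will receive a similar SurveyXact invitation with the end-point questionnaire". Section 18b adds e-mail reminders at 7, 14 and 21 days past the deadline for those who have not answered.

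Section 18b also describes two contacts with people who stop or may have stopped. The first is "If possible, reasons for drop out will be collected from each discontinued participant". The second is a telephone call when synchronisation lapses and drop-out is suspected; its stated purpose is "to either remind them to synchronize the PAM or try to motivate the participant to continue the intervention". Neither contact is said to include an adverse event question or to feed the harms record.

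Section 14 allows for loss: "To account for attrition this study will include 20% more participants", which takes the target from 128 to 154. Section 20 explains how missing outcome data are handled. It does not mention adverse events, and no section defines a harm rate or its denominator.

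**The concern.** Participants are at least 70 and are asked to become more active while wearing a device around the clock. It is plausible that some who stop do so because of an injury or a device problem, and that they are also less inclined to complete an online questionnaire later. Someone who stops in week 3 would be answering about nine weeks after the event (12 − 3 = 9). If harm and non-response go together, the events most relevant to the safety of the intervention are the ones most easily lost, and nothing in the analysis plan would show it.

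The plan already pays for contacts that could catch these events. As written, the caller may remind or encourage, and a reason for stopping may be noted, without anything entering the harms record. The comparison between arms is also exposed. Section 11 schedules seven calls in the experimental arm and describes none for controls (Sections 11.b and 19 do mention taped control sessions), so unprompted reports could differ by arm.

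**Working it through.** **Commitment against mechanism.** Set side by side, the sections give:

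- Section 22: all events after entry are to be recorded.
- Sections 22 and 18a: one retrospective item, by e-mail, on day 84.
- Section 18b: three reminders for that same questionnaire, which reduce non-response but open no new route.
- Section 18b: a call and a drop-out-reason contact, with no link to harms.
- No diary, interim query, adverse event item in the scheduled calls, or query at discontinuation is described.

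A participant who stops and never returns the questionnaire therefore has no stated route into the harms record.

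**The plan's own figure.** The documents give no harm rate to reproduce. The only relevant figure is the sample size, used here for scale. A two-sided t-test at 0.05 (sidedness assumed) with 80% power and a 0.5 SD difference needs 63.77 per arm, so 64 per arm and 128 in total, as stated. The inflation is 128 × 1.20 = 153.6, so 154, also as stated. The allowance is 154 − 128 = 26, and 26/154 = 16.9%.

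**Illustration.** Assume that all 26 are questionnaire non-responders and that none of their events surfaces elsewhere. Let r be the event risk in responders and s the risk in non-responders. Both are assumed; neither is in the documents.

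Overall risk = (128 × r + 26 × s) / 154. Reported risk = r.

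| r | s | Expected events | Overall | Reported |
|---|---|---|---|---|
| 5% | 5% | 6.4 + 1.3 = 7.7 | 5.0% | 5% |
| 5% | 10% | 6.4 + 2.6 = 9.0 | 5.8% | 5% |
| 5% | 20% | 6.4 + 5.2 = 11.6 | 7.5% | 5% |
| 5% | 30% | 6.4 + 7.8 = 14.2 | 9.2% | 5% |
| 5% | 50% | 6.4 + 13.0 = 19.4 | 12.6% | 5% |
| 10% | 5% | 12.8 + 1.3 = 14.1 | 9.2% | 10% |

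With equal risks the rate is not distorted, but 1.3 of 7.7 expected events (17%) are still unrecorded, so the commitment to record all events is not met. At 5% and 20% the unrecorded share is 5.2/11.6 = 45%. The last row shows the error reversing: 10% reported against 9.2% overall.

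Reading the 20% allowance as a loss rate (154 × 0.20 = 30.8, about 31 people) changes little. With r = 5%, s from 5% to 50% gives 5.0% to 0.80 × 5% + 0.20 × 50% = 14.0%.

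**The case against.** The strongest reply is that Section 22 does commit to recording every event, and that describing one query does not rule out others. The call and the drop-out-reason contact in Section 18b are natural places for an event to surface. Discontinued participants are not excluded from the day-84 mailing, and non-responders are reminded three times. Harms are not among the trial's outcomes or hypotheses, and the intervention is non-invasive. Most of this stands and limits the point, but it does not supply a mechanism: the commitment has no stated route for people who stop and do not answer.

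Three stronger readings are tempting, and the documents do not support them.

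- A reader might infer that people who stop are not asked. The plan sends the questionnaire to the participants without excepting anyone, so the risk is that they do not answer.
- A reader might infer that the harm rate is a completers' rate. No rate or denominator is defined, and someone who has stopped wearing the monitor can still answer an online survey. It would be a responders' rate.
- A reader might set the one-sided 95% upper limit for 0 events in 128 (1 − 0.05^(1/128) = 2.3%) against 26/154 = 16.9% as the harm rate still possible. The first is a sampling limit. The second is a worst case in which every non-responder had an event and none came to light. They are not comparable.

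The 26 is also a sample-size inflation, not a forecast of questionnaire non-response. Section 20 keeps drop-outs with at least a week of step data, so loss to the intervention, to the primary analysis and to the survey are different quantities.

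**Conclusion.** The point holds as a gap between a commitment and its mechanism. Followed as written, the plan can lose adverse events among participants who stop and do not return the questionnaire, and any rate based on the item may be too low.

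The size cannot be derived from the documents. The range of 5.0% to 12.6% against 5% reported rests on two assumptions: that the whole allowance of 26 is questionnaire non-response, and that the event risks are those assumed. A lower risk in non-responders would reverse the direction. It would therefore be wrong to state that the rate is too low, or that the arm comparison is biased; the latter would need loss or reporting to differ by arm, which cannot be known in advance. The primary outcome is unaffected. The change is worth making because it is cheap and because, without it, the trial's own harms data could not show where in that range it lies.

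**What to change.** In Sections 18b and 22, state that:

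- the suspected-drop-out call and the drop-out-reason contact include the same adverse event question as the end-point questionnaire, worded identically in both arms, asked before any encouragement to continue, and entered in the harms record with its source and date;
- that single question is e-mailed to participants who discontinue or have not answered by the 21-day reminder, unless they have declined further contact;
- harms are reported by arm over all randomised participants, with the number not answering in each arm, and events from the day-84 questionnaire are shown separately from those found through drop-out contacts.

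Reusing the item carries over its narrower scope, so Section 22 should also say whether the definition or the question governs what is counted.

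The cost is one scripted question in contacts already planned, a one-item e-mail and a few sentences of text, with no visits. The reported harm rate may rise. There is one real downside: participants who are telephoned are asked more often than others, so ascertainment depends partly on adherence and could differ by arm. Recording the source and date and reporting the two sources separately does not remove this, but makes it visible.
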